6.5 Demographics and Baseline Characteristics

Descriptive statistics will be presented by treatment arm for all clinically-relevant baseline demographic, medical history, and clinical characteristic variables.

6.6 Analysis of Study Endpoints

6.6.1 Primary Efficacy Endpoint

The primary efficacy endpoint is defined as assessment of the impact of cochlear implantation versus continued hearing aid use on hearing satisfaction as measured using the SSQ12 at FUV1 (A6 vs B6).

6.6.1.1 Primary Analysis

The primary efficacy endpoint will be assessed with the following hypothesis:

$$H_0: \mu_A \geq \mu_B$$

$$H_a: \mu_A < \mu_B$$

Statistical Analysis Plan		Page 11 of 16
Sponsor Cochlear	Study Hearing Loss in Older Adults	CIP Version 9.0

Where μ_{A6} is the mean SSQ12 score for the cochlear implantation treatment Arm A and μ_{B6} is the mean SSQ12 score for the hearing aid control Arm B at FUV1. The hypothesis will be evaluated using a regression model with treatment and baseline score as covariates. Significance of the treatment effect will be assessed by the p-value for the treatment arm from the regression model.

For analyses using means in the primary endpoints, where there is evidence the model assumptions are not met (e.g. lack of normality of the residuals), transformations or non-parametric tests will be employed.

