8.3 Primary Hypotheses

Cochlear implantation is associated with greater reduction on hearing satisfaction as measured using the Speech, Spatial and Qualities of Hearing (SSQ12) compared to continued hearing aid use at Follow-up Visit 1 (FUV1).

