5.1.1 Primary endpoint

The primary endpoint for the clinical investigation is assessment of the impact of cochlear implantation versus continued hearing aid use on the Speech, Spatial and Qualities of Hearing – short form (SSQ12) test measure at Follow-up Visit 1 (FUV1). Each subject will serve as their own control.

Data from a clinical investigation on the Cognitive Performance of Severely Hearing-impaired Older Adults Before and After Cochlear Implantation (1) was used to estimate the effect of cochlear implantation on the SSQ12.

The sample size estimation for the primary endpoint is based on the mean (SD) change of 3.0 (1.8) for the change in SSQ12 score reported in Claes et al. (pre-operative to postoperatively at six months post-activation) (1). The sample size estimation assumes that the observed mean change and standard deviation of change reported by Claes for SSQ12 is representative of the corresponding values for the clinical population under investigation.

Statistical Analysis Plan		Page 8 of 16
Sponsor Cochlear	Study Hearing Loss in Older Adults	CIP Version 9.0

Sample size calculations were conducted using PASS statistical software under the following general assumptions:

1. Two-sample t-test
2. Two-sided 0.025 α levels
3. 80% power
4. No accounting for attrition or lost to follow up

In order to achieve 80% power with an effect size of 1.667 ($d = (\mu_A - \mu_B)/\sigma$) with 20% attrition, a sample size of 12 per arm would be needed respectively. Therefore, a sample size of 60 supports the effect sizes observed in Claes et al. (2018) as well as possible attrition.

6 Statistical Analyses

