6.1.3 Statistical Significance

Unless otherwise specified, hypothesis testing will be performed at the two-sided 0.05 significance level (or equivalently at a one-sided 0.025 level). P-values will be rounded to three decimal places. If a p-value is less than 0.001 it will be reported as "<0.001". If a p-value is greater than 0.999, it will be reported as ">0.999".

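### The SAP's only written H0/Ha has the implant arm scoring lower on SSQ12, opposite in sign to its own sample-size effect, and neither document says which direction of SSQ12 is better

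*SAP*

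**What the plan says.** **Hypothesis.** SAP 6.6.1.1 says "The primary efficacy endpoint will be assessed with the following hypothesis" and displays H0: μA ≥ μB and Ha: μA < μB. The text below the display explains that the first mean "is the mean SSQ12 score for the cochlear implantation treatment Arm A" and that the second belongs to the hearing aid control, Arm B, both at FUV1. The model is a regression on treatment and baseline score, and "Significance of the treatment effect will be assessed by the p-value for the treatment arm from the regression model". No favourable sign is named for the treatment coefficient.

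**Planned effect.** The sizing in SAP 5.1.1 is "based on the mean (SD) change of 3.0 (1.8) for the change in SSQ12 score", from before implantation to six months after activation. It continues: "In order to achieve 80% power with an effect size of 1.667", and prints the signed definition d = (μA − μB)/σ next to that value.

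**Protocol hypothesis.** Protocol 8.3 reads: "Cochlear implantation is associated with greater reduction on hearing satisfaction", compared with continued hearing aid use at FUV1.

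**Alpha.** The sizing assumptions in SAP 5.1.1 list "Two-sided 0.025". SAP 6.1.3 says that, unless otherwise specified, "hypothesis testing will be performed at the two-sided 0.05 significance level (or equivalently at a one-sided 0.025 level".

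**Scoring direction.** It is not stated. Protocol 9.2.3.5 describes the SSQ12 as a measure of auditory disability. The objectives and endpoints in both documents call the outcome hearing satisfaction.

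**Other hypotheses.** SAP 6.6.2 and 6.7 rule out formal hypothesis testing for the secondary and ancillary analyses. SAP 6.7.1.1 nevertheless sets a Bonferroni level of 0.01, but no H0 or Ha is written there.

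**The concern.** The H0/Ha pair in SAP 6.6.1.1 is the only one the SAP writes down, and it defines what counts as success. As printed, success means a lower SSQ12 mean with the implant, while the trial is sized on a higher one. Protocol 8.3, read literally, predicts harm.

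A reader cannot settle this from the documents, because the one fact needed, whether a higher SSQ12 is better or worse, is missing and the two descriptions of the construct point in opposite directions.

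At stake is the prespecified direction of the primary claim in an unblinded trial (SAP 4.2). If the implant arm scores higher by the planned amount, either the result is reported against a hypothesis that names the opposite, or the direction is changed after the data are seen.

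**Working it through.** **Step 1: reproduce the plan's own figure.**
- d = 3.0/1.8 = 1.667, as printed.
- Exact two-sample t-test (noncentral t), two-sided 0.025, 80% power: 8 per arm gives 0.784 and 9 per arm gives 0.844, so 9 evaluable are needed. 9/0.8 = 11.25, which rounds up to 12, the SAP's figure.
- At two-sided 0.05, 7 per arm suffice, and 7/0.8 = 8.75 rounds up to 9.
- The SAP's 12 per arm was therefore reached at two-sided 0.025, not at the 0.05 of SAP 6.1.3.
- A two-sided calculation uses only |d|, so the figure does not depend on the sign.

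**Step 2: compare the signs.**

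| Place | Statement | Direction |
|---|---|---|
| SAP 6.6.1.1 | Ha: μA < μB | Implant arm lower |
| SAP 5.1.1 | (μA − μB)/σ = +1.667 | Implant arm higher |
| Protocol 8.3 | Greater reduction with implant | Implant arm lower, if the reduction is read as a fall in score |

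- *If higher is better:* the sizing describes benefit, while Ha and protocol 8.3 both describe harm.
- *If higher is worse (a disability score):* Ha describes benefit, and a fall in the score would fit it, but the printed sign of d then describes harm. The words of protocol 8.3 also still predict less satisfaction.

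On neither reading do all three agree. That higher is better is an inference from the positive planned effect and the satisfaction label. The primary objective (protocol 8.1, SAP 3.1) has no direction and is not contradicted.

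**Step 3: what follows for the test.**

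Inputs: 60/2 = 30 per arm; 30 × 0.8 = 24 per arm after the SAP's 20% attrition; d = 1.667 taken as the between-arm difference, as the SAP does. Noncentrality = d × √(n/2) = 1.667 × √12 = 5.77 at n = 24, and 1.667 × √15 = 6.45 at n = 30, with 2n − 2 degrees of freedom. This is the unadjusted t-test, as in the SAP's sizing.

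| Effect | n per arm | Ha as displayed, one-sided 0.025 | Two-sided 0.05 | Two-sided 0.025 |
|---|---|---|---|---|
| d = 1.667 (planned) | 24 | 1.3 × 10⁻¹⁴ | 0.9999 | 0.9996 |
| d = 1.667 (planned) | 30 | 4.7 × 10⁻¹⁷ | >0.9999 | >0.9999 |
| d = 0.833 (assumed, half) | 24 | 8.4 × 10⁻⁷ | 0.81 | 0.71 |
| d = 0.833 (assumed, half) | 30 | 1.4 × 10⁻⁷ | 0.89 | 0.82 |

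At the SAP's stated minimum of 28 per arm and the planned effect, the corresponding values are 3.0 × 10⁻¹⁶, >0.9999 and 0.9999.

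**The case against.** The strongest reply is that nothing operative changes. The decision rests on the treatment p-value from the regression, and the default in SAP 6.1.3 is two-sided 0.05, so the p-value, the power and the sample size are the same whichever way Ha is written. This stands. The very small probabilities in the table arise only if the displayed hypothesis is tested literally, and no section instructs that. However, SAP 6.1.3 applies only unless otherwise specified and equates its level with a one-sided 0.025 test, and SAP 6.6.1.1 displays a one-sided hypothesis, so the literal reading is not excluded.

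Second, the 1.667 comes from a single-arm before-to-after change and may have been meant as a magnitude inserted beside a generic formula. That is possible, but the SAP prints the signed formula. Even with an unsigned d, Ha and protocol 8.3 cannot be interpreted without a scoring direction.

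Third, the documents establish inconsistency, not which statement is wrong. This also stands: two of the three point to a lower value in Arm A, and d is the exception. It is why the scoring direction has to be settled before anything is rewritten. The SSQ12 is a cited instrument and the SAP is to be read with the case report forms, which are not available here, so the direction may be recorded elsewhere. That would not remove the conflict between SAP 5.1.1 and 6.6.1.1.

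**Conclusion.** The concern holds and needs correcting before analysis. The trial's only written H0/Ha is opposite in sign to the effect on which the trial was sized, the protocol's hypothesis is worded as a loss of satisfaction, and no scoring direction is given that could settle the matter.

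This is an error of specification and reporting, not a loss of power. Under the two-sided 0.05 default the cost in power is nil. The planned benefit could not reject H0 only under a literal one-sided test. The sign conflict rests on the SAP's printed formula for d; the power figures also rest on its use of 3.0/1.8 as a between-arm effect. The half-effect rows are an assumption, shown for range.

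**What to change.** 1. State the SSQ12 scoring direction in the SAP and in protocol 9.2.3.5.
2. Once higher-is-better is confirmed, which is what the sizing implies, rewrite SAP 6.6.1.1 in one of two ways. Either use H0: μA6 ≤ μB6 against Ha: μA6 > μB6 at one-sided 0.025, or use a two-sided test of equality at 0.05 with benefit claimed only if the baseline-adjusted Arm A minus Arm B coefficient is in the favourable direction. If lower is confirmed as better, keep Ha and correct the sign of d in SAP 5.1.1 instead.
3. In protocol 8.3, replace the predicted reduction with a greater improvement in hearing satisfaction.
4. In the same edit, reconcile the two-sided 0.025 of SAP 5.1.1 with the two-sided 0.05 of SAP 6.1.3 and name one alpha and sidedness for the primary test. The planned effect keeps power of at least 0.9996 at 24 per arm under either, so the sample size need not change on that account. At half the planned effect the choice matters more: 0.81 against 0.71 at 24 per arm.

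The cost is wording in SAP 5.1.1 and 6.6.1.1 and in protocol 8.3 and 9.2.3.5, made by amendment before the analysis. The sample size, regression model and data collection do not change.

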6.6.2 Secondary Efficacy Endpoint

The secondary efficacy endpoint is defined as assessment of the impact of cochlear implantation versus continued hearing aid use on cognition with a Cogstate® computerized battery of neuropsychological tests at FUV1 (A6 vs B6).

The Cogstate computerized battery results will be presented using descriptive statistics only and analyzed using a t-test to compare the mean score of the cochlear implant Arm A to that of the hearing aid control Arm B. As the analyses for the secondary efficacy endpoint are exploratory in nature, there will be no adjustment for multiple comparisons and no formal hypotheses testing. The results from the analyses for the secondary efficacy endpoint may be used for calculation of sample size in future clinical investigations.

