9.2.1.2 Cogstate computerised test battery

The Cogstate® computerised test battery is a self-administered, iPad-based neuropsychological measure of processing speed, attention, visual learning, working memory and executive function. The Cogstate computerised test battery for the current clinical investigation consists of the Cogstate Brief Battery™ and the Groton Maze Learning Test.

The Cogstate Brief Battery (CBB) provides a measure of four core cognitive domains: processing speed, attention, visual learning and working memory. The CBB consists of the Detection Test, Identification Test, One Card Learning Test and One Back Test. The Detection test measures processing speed using a simple reaction time paradigm. The Identification test measures attention using a choice reaction time paradigm. The One Card Learning test measures visual memory using a pattern separation paradigm. The One Back test measures working memory using an n-back paradigm. For all tests in the CBB, a playing card is presented on the screen and the participant is encouraged to work as quickly as they can and be as accurate as possible.

The Cogstate Groton Maze Learning Test measures executive function using a maze learning paradigm. A 28-step pathway is hidden among these tiles. The participant must move one step at a time from the start toward the end by touching a tile next to their current location. If the correct move is made a green checkmark appears and if the move is incorrect a red cross is revealed. Once completed, they are returned to the start location to repeat the test and must try to remember the

pathway they have just completed. The outcome measure is the total number of errors made in attempting to learn the same hidden pathway on five consecutive trials during a single session.

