6.7.1.2 Tertiary Analyses

All tertiary analyses will be presented using descriptive statistics and analyzed using a t-test to compare the mean score of the cochlear implant Arm A to that of the hearing aid control Arm B at various time points. As these tertiary analyses are exploratory in nature, there will be no adjustment for multiple comparisons, no formal hypotheses testing and no statement of statistical significance.

Investigating treatment effect on:

- Neuropsychological outcomes:
 - Cogstate¹:
 - ☒ Detection Test – speed of performance
 - ☒ Groton Maze Learning Test – number of errors
 - ☒ Identification Test – speed of performance
 - ☒ One Card Learning Test – accuracy of performance
 - ☒ One Back Test – speed of performance
 - A6 vs B6 (treatment effect)
 - A0 vs B0 (population)
 - A6 vs B12 (6 months post-CI)
 - A12 vs B18 (12 months post-CI)
 - A0 vs A6 vs A12 (longitudinal treatment effect)
 - B6 vs B12 vs B18 (longitudinal treatment effect)
 - HI-MoCA:
 - ☒ A6 vs B6 (treatment effect)
 - ☒ A0 vs B0 (population)
 - ☒ A6 vs B12 (6 months post-CI)

¹ A sensitivity analyses will be conducted with test data integrity failures excluded if the integrity failure rate is greater than 10%.

Statistical Analysis Plan		Page 13 of 16
Sponsor	Study	CIP Version
Cochlear	Hearing Loss in Older Adults	9.0

- ☒ A12 vs B18 (12 months post-CI)
- ☒ A0 vs A6 vs A12 (longitudinal treatment effect)
- ☒ B6 vs B12 vs B18 (longitudinal treatment effect)
- Psychosocial measures:
 - UCLA Loneliness Scale:
 - ☒ A0 vs B0 (population)
 - ☒ A6 vs B12 (6 months post-CI)
 - ☒ A12 vs B18 (12 months post-CI)
 - ☒ A0 vs A6 vs A12 (longitudinal treatment effect)
 - ☒ B6 vs B12 vs B18 (longitudinal treatment effect)
 - Geriatric Depression Scale (GDS):
 - ☒ A0 vs B0 (population)
 - ☒ A6 vs B12 (6 months post-CI)
 - ☒ A12 vs B18 (12 months post-CI)
 - ☒ A0 vs A6 vs A12 (longitudinal treatment effect)
 - ☒ B6 vs B12 vs B18 (longitudinal treatment effect)
- Audiometric measures:
 - HHIE-S:
 - ☒ A0 vs B0 (population)
 - ☒ A6 vs B12 (6 months post-CI)
 - ☒ A12 vs B18 (12 months post-CI)
 - ☒ A0 vs A6 vs A12 (longitudinal treatment effect)
 - ☒ B6 vs B12 vs B18 (longitudinal treatment effect)
 - SSQ12:
 - ☒ A0 vs B0 (population)
 - ☒ A6 vs B12 (6 months post-CI)
 - ☒ A12 vs B18 (12 months post-CI)
 - ☒ A0 vs A6 vs A12 (longitudinal treatment effect)
 - ☒ B6 vs B12 vs B18 (longitudinal treatment effect)

Statistical Analysis Plan		Page 14 of 16

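### SAP 6.6.2 does not name the Cogstate variables behind the secondary endpoint, repeats a tertiary comparison, contradicts itself on testing, and leaves the POV2 baseline unused

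*SAP*

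**What the plan says.** SAP 6.6.2 sets the endpoint in general terms: "The secondary efficacy endpoint is defined as assessment of the impact of cochlear implantation versus continued hearing aid use on cognition", using the Cogstate battery at FUV1 (A6 vs B6). For the analysis it states: "The Cogstate computerized battery results will be presented using descriptive statistics only and analyzed using a t-test to compare the mean score" of Arm A with that of Arm B. It calls this work exploratory and adds that "there will be no adjustment for multiple comparisons and no formal hypotheses testing". It also allows the results to be used for sizing later studies.

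Protocol 9.2.1.2 describes the battery as the Cogstate Brief Battery plus the Groton Maze Learning Test. On the first part: "The CBB consists of the Detection Test, Identification Test, One Card Learning Test and One Back Test". It gives an outcome measure only for the maze: "The outcome measure is the total number of errors made in attempting to learn the same hidden pathway on five consecutive trials".

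SAP 6.7.1.2 lists one outcome per test: three of speed (for example "Detection Test – speed of performance"; also Identification and One Back), one of accuracy ("One Card Learning Test – accuracy of performance") and one error count (Groton Maze). It compares these by t-test at several time points, including A6 vs B6, and rules out any statement of statistical significance.

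The visit table in SAP 6.1.2 labels the POV2 Cogstate score as the baseline (A0 or B0). SAP 6.6.1.1 analyses the primary endpoint by regression on treatment and baseline score.

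**The concern.** Read alone, 6.6.2 leaves an analyst with four questions.

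- **Which variable?** The text refers to one score, the battery yields five outcomes of three kinds, and neither document defines a total or composite or names a key outcome.
- **Which level?** If the five outcomes of 6.7.1.2 are meant, the same A6 vs B6 t-tests are both secondary and tertiary. The tertiary text forbids statements of significance; the secondary text does not repeat that limit.
- **Described or tested?** The paragraph promises descriptive statistics only, then a t-test, then no formal hypothesis testing.
- **Why no baseline?** The battery is given before the intervention at both POV1 and POV2. Protocol section 7 says this is to limit learning effects. A t-test on FUV1 scores then leaves the POV2 result out.

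At stake is a cognition result that can be reported in more than one way in an unblinded trial, with wider intervals than the collected data allow. Protocol 6.1 presents the trial as the first randomised comparison of implantation and hearing aids on cognitive function, so the result will attract attention whatever its formal status.

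**Working it through.** **1. The plan's own figure.** The SAP's only calculated sample size is for SSQ12: d = 3.0/1.8 = 1.667, two-sided alpha 0.025, 80% power. A two-sample t-test needs 9 per arm, and 9/0.8 = 11.25, so 12 per arm after 20% attrition. This reproduces the stated 12, but does not concern Cogstate, for which the SAP gives no effect, SD or power.

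**2. What the score most likely means.** SAP 6.7.1.1 uses the same phrase about comparing arm mean scores for five unrelated measures (UCLA, GDS, CNC words, AzBio, HUI-III), and 6.7.1.2 uses it for the five Cogstate outcomes. In both places it can only mean the arm mean of each measure. Section 6.6.2 also speaks of analyses in the plural and mentions multiple comparisons. The natural reading is therefore five separate comparisons. On that reading, the secondary analysis and the Cogstate A6 vs B6 row in 6.7.1.2 are the same analysis on the same data.

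**3. What baseline adjustment is worth.** Let ρ be the correlation between a test's POV2 and FUV1 scores. A t-test on FUV1 scores has residual variance σ²; regression on arm and POV2 has σ²(1 − ρ²). The effective standardised effect is d/√(1 − ρ²), and the noncentrality is that effect times √(n/2).

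Inputs:
- n = 24 per arm, from 60 × 0.8 / 2 (SAP 4 and the 20% attrition in SAP 4.1)
- d = 0.4 per test, assumed
- ρ = 0.5 to 0.8, assumed, with 0.3 as a pessimistic check
- two-sided 0.05, the default in SAP 6.1.3, used here only as a yardstick for precision

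| Analysis | 1 − ρ² | Effective d | Noncentrality (× √12) | Power |
|---|---|---|---|---|
| t-test at FUV1 | 1 | 0.400 | 1.39 | 27% |
| Regression, ρ = 0.3 | 0.91 | 0.419 | 1.45 | 30% |
| Regression, ρ = 0.5 | 0.75 | 0.462 | 1.60 | 35% |
| Regression, ρ = 0.8 | 0.36 | 0.667 | 2.31 | 62% |

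Residual variance falls by 25% (ρ = 0.5) to 64% (ρ = 0.8). That equals 1/0.75 = 1.33 to 1/0.36 = 2.78 times the sample size.

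**4. Whether a composite would be better.** Average five standardised, sign-aligned tests with common correlation r, of which k respond with d = 0.4. The composite effect is 0.4 × (k/5) / √((1 + 4r)/5). The divisor is √0.36 = 0.600 at r = 0.2 and √0.68 = 0.825 at r = 0.6. Power with 24 per arm, without baseline adjustment:

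| Domains responding | r = 0.2 | r = 0.6 |
|---|---|---|
| 1 | 7% | 6% |
| 2 | 15% | 10% |
| 3 | 27% | 17% |
| 4 | 44% | 26% |
| 5 | 62% | 38% |

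A single responding test has 27%. At r = 0.2 the composite only draws level at three domains; at r = 0.6 it is still slightly behind at four. It is a trade-off.

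**The case against.** The strongest reply is that this is a drafting gap. The score is the arm mean of each test, the five outcomes are named in 6.7.1.2, and the analysis is openly exploratory. Reporting domain by domain serves an objective worded simply as assessing cognition, and means and SDs for five outcomes are enough for a later trial to choose its endpoint.

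Most of that stands, and it rules out three stronger readings:

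- *The score does not exist, or unlike units would be averaged.* The documents leave the score undefined; they do not say that the instrument lacks one, and nothing proposes averaging raw results. Errors and accuracy do run in opposite directions, but that matters only if someone builds a composite.
- *False positives are uncontrolled.* Five independent tests at 0.05 would give 1 − 0.95⁵ = 22.6% for at least one. That figure presumes significance would be declared test by test, and 6.6.2 disclaims formal testing.
- *A composite is required.* Step 4 shows that it loses power if the effect sits in one or two domains. Protocol 9.2.1.2 describes the tests by distinct domains, so that case cannot be dismissed.

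The reply does not answer the missing cross-reference, the duplicate row, the internal contradiction or the unused baseline. Exploratory status excuses the absence of alpha control. It does not justify an unnamed variable or a less precise estimator when the covariate is already collected.

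**Conclusion.** The point holds as one of specification and precision. Section 6.6.2 should name its variables, sit at one level of the hierarchy, say consistently what will be reported, and use POV2. The first three follow from the text alone. The fourth has a size: power per comparison rises from 27% to about 35% to 62%, resting on an assumed d of 0.4, 24 per arm and a baseline correlation of 0.5 to 0.8. At a correlation of 0.3 the gain is only three percentage points. The documents give neither the effect nor the correlation.

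The primary endpoint is unaffected. A reader might infer that the cognition objective cannot be answered at all; the documents do not support that, because five usable outcomes are listed. The results remain exploratory, with no claim of significance.

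**What to change.** In SAP 6.6.2:

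1. Name the five outcomes now in 6.7.1.2 as the exploratory secondary outcomes, and state the scale and the direction of benefit of each. The documents do not give the scaling of the three speed outcomes.
2. Replace the t-test with a regression of each FUV1 outcome on arm and that test's own POV2 value, as in 6.6.1.1. Report the adjusted difference with a 95% confidence interval.
3. Delete the word 'only', and carry over from 6.7.1.2 the exclusion of any statement of significance and the footnoted sensitivity analysis for test integrity failures.

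In SAP 6.7.1.2, remove the Cogstate A6 vs B6 row and keep the other time-point comparisons.

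Optionally, add a standardised, sign-aligned composite as a summary beside the five results, noting that it helps only if the effect is spread across most domains.

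The cost is SAP wording and minor programming; POV2 scores are already collected. Because SAP 6.4 imputes only SSQ12, a subject without a POV2 score on a test drops out of that comparison, and the number analysed should be shown.

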7 JUSTIFICATION FOR THE DESIGN OF THE CLINICAL INVESTIGATION

We propose a randomized controlled trial design whereby up to sixty (60) participants with severe-to-profound hearing loss are randomized 1:1 to an immediate cochlear implant (CI) intervention (Arm A) versus a hearing aid (HA) control intervention (Arm B). The immediate CI treatment arm will be implanted with either the Cochlear Nucleus® Profile™ Slim Modiolar (532) cochlear implant or the Cochlear Nucleus® Profile™ Plus CI632 cochlear implant with Slim Modiolar electrode. The HA control intervention provides a comparison arm representing standard clinical care for conventional amplification (HAs). Randomization seeks balance between the two arms. The control arm will also receive the CI intervention (Nucleus CI532 or CI632 implant) after a watchful waiting delay period of 6 months post baseline. Both arms will receive the neuropsychological battery twice before the intervention (once at screening and again at baseline) to minimize the impact of learning effects on analyses of post-intervention cognitive change.

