9.3.5 Preoperative Visit 2 (POV2) - Baseline

Preoperative visit 2 (POV2) baseline will occur 4-6 weeks post POV1 (+/- 2 weeks) to enable scheduling of surgery for Arm A subjects. Both Arm A and Arm B subjects will complete POV2 with appropriately fit hearing aids and glasses (if required). The full neuropsychological battery in addition to the audiology, psychosocial, physical, and quality of life metrics will be completed as described in Section 9.2. Speech recognition will be assessed in the everyday listening condition (aided bilaterally) and the ear to be implanted listening conditions with the contralateral ear plugged. Datalogs will be retrieved for the hearing aid.

Medical history will be completed minimally via the ACE 27 index. The Investigator or appropriately delegated staff may add additional otologic history (hearing history) which they deem relevant to the study.

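### Cogstate at FUV1, the only secondary endpoint, is compared between arms by an unadjusted t-test although a POV2 baseline score exists in both arms; adjusting for it would gain precision at no data cost

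*SAP*

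**What the plan says.** SAP 6.6.2 names one secondary efficacy endpoint, Cogstate at FUV1 (A6 vs B6). The battery is to be "analyzed using a t-test to compare the mean score of the cochlear implant Arm A" with that of Arm B, the hearing aid control. No baseline term appears. The same section calls the analysis exploratory and states that "there will be no adjustment for multiple comparisons and no formal hypotheses testing", and adds that the results "may be used for calculation of sample size in future clinical investigations".

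The primary endpoint, measured in the same subjects at the same visit, is handled differently in SAP 6.6.1.1: "The hypothesis will be evaluated using a regression model with treatment and baseline score as covariates".

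A Cogstate baseline exists. The schedule in Protocol section 5 places the battery at POV1 and POV2 for both arms. Protocol 9.3.5 says of POV2: "The full neuropsychological battery in addition to the audiology, psychosocial, physical, and quality of life metrics will be completed". SAP 6.1.2 labels the POV2 Cogstate score A0 or B0. Protocol section 7 explains that the battery is given twice before the intervention "to minimize the impact of learning effects on analyses of post-intervention cognitive change".

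SAP 6.7.1.2 lists five Cogstate outcomes (three speed measures, one accuracy measure, one error count) and no composite. It repeats A6 vs B6 as a t-test. The baseline score enters only A0 vs B0 and the Arm A series A0, A6, A12. The Arm B series starts at B6.

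**The concern.** The trial collects a pre-intervention Cogstate score in every subject and then leaves it out of the one comparison that estimates the treatment effect on cognition. No planned between-arm Cogstate contrast at FUV1 uses it, and no planned analysis measures Arm B's change from B0 to B6. Yet the protocol justifies the repeated testing by reference to analyses of change, and the SAP adjusts SSQ12 for baseline without saying why Cogstate should differ.

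Baseline cognition can vary widely in this population. Eligibility covers ages 65 to 85 and HI-MoCA scores of 20 or more, from mild impairment to normal. Randomization is stratified by site only (SAP 4.1), so nothing in the design balances cognition between arms. Missing Cogstate scores are not imputed (SAP 6.4), so the groups actually compared may drift further apart. At stake are the width of the interval around the cognition result and its usefulness for planning later trials.

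**Working it through.** **The plan's own figure.** Neither document gives a sample size, SD, effect size or power for Cogstate. The only sample-size figure is for SSQ12 (SAP 5.1.1): d = 3.0/1.8 = 1.667, two-sided alpha 0.025, 80% power. The exact two-sample t calculation gives 9 per arm (power 84.4%), and 9/0.8 = 11.25, rounded up to 12. The stated 12 per arm reproduces. It says nothing about precision for Cogstate.

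**Inputs.**
- n = 28 per arm, the minimum in SAP section 4. As a lower case, 60 subjects less the 20% attrition in SAP 4.1 leaves 48, or 24 per arm.
- Alpha two-sided 0.05, from SAP 6.1.3, used here for illustration only, because 6.6.2 plans no formal test.
- r, the baseline-to-FUV1 correlation: not in the documents. Assumed range 0.3 to 0.8. It may differ across the five tests.

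**Formulas.** With σ the SD of the FUV1 score:
- Variance of the unadjusted difference: 2σ²/n.
- Variance of the baseline-adjusted difference: about (1 − r²) × 2σ²/n.
- Share of information lost by not adjusting: r².
- Equivalent total size of an unadjusted trial: 2n/(1 − r²).
- Detectable difference and power: noncentral t with 2n − 2 df unadjusted; with adjustment, 2n − 3 df and a small-sample factor of (2n − 4)/(2n − 3) on the information.

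**Results, 28 per arm.**

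| r (assumed) | Information lost | Unadjusted trial of equal precision (total) | Detectable at 80% power | Power for an assumed 0.5 SD |
|---|---|---|---|---|
| no adjustment | – | 56 | 0.76 SD | 45% |
| 0.3 | 9% | 56/0.91 = 62 | 0.74 SD | 48% |
| 0.5 | 25% | 56/0.75 = 75 | 0.67 SD | 56% |
| 0.7 | 49% | 56/0.51 = 110 | 0.55 SD | 72% |
| 0.8 | 64% | 56/0.36 = 156 | 0.46 SD | 86% |

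With 24 per arm the detectable difference is 0.83 SD unadjusted, 0.72 SD at r = 0.5 and 0.60 SD at r = 0.7.

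**Break-even.** At 24 per arm the price of one covariate is a variance factor of 45/44 = 1.023. Adjustment gains once r² exceeds 1 − 44/45 = 0.022, that is, once r exceeds about 0.15.

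**Chance imbalance.** The standard error of a baseline mean difference is √(2/24) = 0.29 SD, or √(2/28) = 0.27 SD. A difference of at least 0.3 SD in either direction then has probability about 30% or 26%. It carries over to FUV1 multiplied by r: at r = 0.5 to 0.7, a 0.3 SD imbalance shifts the comparison by 0.15 to 0.21 SD.

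**The case against.** The strongest reply is that this is an exploratory comparison with no formal test, so no confirmatory claim depends on it, and that the t-test is a valid estimator. Both points stand. They limit the weight of the concern but do not remove it, because an exploratory estimate meant to inform later trials is judged mainly by its precision.

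Four stronger readings are tempting and are not supported.

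- A reader might infer that leaving out the baseline lets learning effects bias the result. Learning is addressed by the double pre-intervention testing, which works through exposure whether or not the score is modelled, and by the concurrent control arm on the same testing schedule to FUV1. Learning common to both arms cancels.
- A reader might state a fixed loss, such as a quarter to a half of the information. That needs r between about 0.5 and 0.71, which the documents do not supply for any of the five tests.
- A reader might say that baseline imbalance passes undiminished into the comparison. It passes in proportion to r, and the t-test's standard error already reflects that variability. The planned A0 vs B0 comparison would also show an imbalance, though it would not correct for it.
- A reader might say that the planned output would give later trials a wrong SD. The raw FUV1 SD is the right input for an unadjusted design and a conservative one for an adjusted design. What is missing is r: the SAP does not plan to report it.

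**Conclusion.** The point holds as a free improvement. The plan omits an available covariate from its only secondary between-arm comparison, and nothing elsewhere in the SAP makes up for it. The estimate remains unbiased under randomization with complete data. The loss is r² of the information: 9% to 64% over the assumed range of r from 0.3 to 0.8, with any r above about 0.15 favouring adjustment even at 24 per arm. The direction is secure for any plausible repeat cognitive measure. The size is not, because it rests on correlations that the documents do not give and that may differ by test. No conclusion about the primary endpoint is affected.

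**What to change.** In SAP 6.6.2, replace the t-test with a regression of each FUV1 Cogstate outcome on treatment arm and that outcome's POV2 score, matching the primary model. Site, the stratification factor, may be added but is optional. Report the adjusted difference with a 95% interval, together with the residual SD and the baseline-to-FUV1 correlation, so that a later trial can be sized for either an adjusted or an unadjusted design.

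Apply the same model to the Cogstate A6 vs B6 contrasts in 6.7.1.2. If it is extended to other A6 vs B6 contrasts, use each measure's own A0/B0 visit from SAP 6.1.2; for HI-MoCA that is POV1, not POV2.

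A t-test on change scores would be a weaker remedy. Its variance factor is 2(1 − r), which improves on the unadjusted comparison only when r exceeds 0.5 (1.4 at r = 0.3; 0.6 at r = 0.7, against 0.51 for the regression).

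The cost is SAP wording only; the data are already scheduled. The sentence needs editing in any case, since it promises descriptive statistics alone and a t-test together.
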